### 11.1 Extent of exposure

There are 4 different concepts for calculating exposure during the double-blind treatment period.

1. This approach will look at the number of doses received, which is defined as dosing days.

Days with 2 injections (i.e. at Week 0, 2 and 4) are counted as 1 dosing day if either injection is given).

2. For the CZP 200mg and placebo treatment arms, duration of exposure to study medication will be calculated as:

Date of last administration of double-blind CZP 200mg or placebo study medication – date of first administration of CZP 200mg or placebo study medication + 14 days (14 days are included in this definition as this is the dosing interval for maintenance of subjects).

If a subject dies during the exposure period (first injection to last injection + 14 days), the exposure period will end with the death date.

For subjects discontinuing from the study before Week 52, the 2-week period after last double-blind injection will be utilized.

3. For the study exposure of a subject, 5 half-lives of CZP will be taken into account. Hence, a subject will be regarded as being exposed to study drug from first double-blind injection to last double-blind injection + 70 days. The days of drug holidays beyond 70 days will be subtracted.

If a subject dies during the exposure period (1st injection to last injection + 70 days), the exposure period will end with the death date.

For subjects discontinuing from the study before Week 52, the 70 day period after last injection will be utilized.

4. This approach will be the nearly identical to approach 2. However, exposure will be censored at the first occurrence of the AE to be considered for analysis (a separate calculation has to be performed for each preferred term). The different exposure duration for the respective AEs will only be displayed in the AE tables for exposure-adjusted incidences and will not be summarized in the exposure table.

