Exposure to the OL-CZP treatment will also be calculated using the above 4 methods considering only dosing during the time the subject is receiving OL-CZP study medication prior to Start of SFE. Exposure during the SFE period will be calculated using methods 2, 3 and 4 assuming first dose in the SFE period starts when the subject takes their loading dose/first dose of OL-CZP in the SFE period and ends when the subject has their last administration of study medication (or if missing, the date of withdrawal from the SFE). Total CZP incl DB and OL

exposure will be calculated using all 4 methods, by summing the exposure to CZP during the double-blind and OL- CZP periods. Total CZP incl DB, OL, and SFE OL will be calculated using methods 2, 3 and 4, by summing the exposure to CZP during the double-blind, OL-CZP and SFE periods. Note that for Total CZP incl DB, OL, and SFE OL method 1 will not be calculated as the SFE period does not collect data on dose administration. Exposure to OL-OT will not be calculated.

For the first 3 approaches, tables will summarize exposure for the placebo, CZP 200mg Q2W, OL-CZP treatment groups (split by the treatment taken during the double-blind period), SFE OL-CZP, Total CZP incl DB and OL and Total CZP incl DB, OL, and SFE OL (for methods 2 and 3 only).

The following doses will be presented in a listing:

- very first dose in the study, the very last dose in the study and the difference between them
- last dose in the DB period (i.e. last DB dose or last OL dose), the last SFE dose and the difference between them.

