Because subjects will be able to adjust background medications during the study, some additional AE tables may be prepared in which events occurring while on certain background medications will be summarized. The list of these supportive tables is expected to be as follows but other subsets of TEAEs may be explored:

- TEAEs reported after starting a new biologic, but within 10 weeks of stopping CZP

- TEAEs reported one month after changing NSAID type
- TEAEs reported three months after changing or adding a DMARD
- TEAEs reported within one month of an addition of oral corticosteroids or 50% increase in dose

The purpose of these tables will be to assess whether any observed treatment differences in the AE profile may be due, in part, to these prespecified background medications.

A TEAE table will also be presented for the ‘anti-CZP antibody status’ subgroup defined in [Section 10](#). Only subjects exposed to CZP and only TEAEs occurring after first dose of CZP will be considered. A further column will be presented summarizing TEAEs occurring after the onset of the positive antibody status. The EAIR will be presented in addition to the associated 95% CI, and the EAER.

The TEAE incidence rates will also be adjusted for exposure (as calculated using methods 3 and 4 in [Section 11.1](#)) and reported by 100 subject years of exposure. Two approaches will be applied to adjust for exposure. One will only use the first occurrence of an AE with corresponding exposure (EAIR) and the second approach will use all AEs and the entire exposure (EAER).

For the EAIR, the first occurrence of an TEAEs for a certain treatment group will be utilized (either placebo or CZP 200mg Q2W for the double-blind period or OL-CZP) and divided by the sum of exposure of all subjects in the respective treatment group, where subjects experiencing the respective AE will be censored at the time of occurrence of the AE. The EAIR will be multiplied by a factor of 100 to give a rate per 100 subject-years.

For the EAER, all TEAEs for a certain treatment group will be utilized (either placebo or CZP 200mg Q2W for the double-blind period or OL-CZP) and divided by the sum of exposure of all subjects in the respective treatment group. The EAER will be multiplied by a factor of 100 to give a rate per 100 subject-years.

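### The summing rule for the Total CZP exposure columns includes method 4, which conflicts with the censor-once definition of the EAIR and leaves the pooled denominator undefined

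*SAP*

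**What the plan says.** SAP Section 11.1 defines four exposure concepts. Method 4 starts from method 2 (last dose plus 14 days): "This approach will be the nearly identical to approach 2". The difference is that "exposure will be censored at the first occurrence of the AE to be considered for analysis". The section adds that method-4 durations appear only in the AE tables of exposure-adjusted incidence, not in the exposure table.

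Section 11.1 then applies the methods period by period. OL-CZP exposure is worked out "considering only dosing during the time the subject is receiving OL-CZP study medication prior to Start of SFE", and SFE exposure has its own start and end.

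For the narrower pooled column, which leaves out the SFE, "exposure will be calculated using all 4 methods, by summing the exposure to CZP during the double-blind and OL- CZP periods". For the wider one, "Total CZP incl DB, OL, and SFE OL will be calculated using methods 2, 3 and 4, by summing the exposure to CZP" over the double-blind, OL-CZP and SFE periods. Method 4 is included in both rules.

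Section 11.2 defines the EAIR. In the numerator, "the first occurrence of an TEAEs for a certain treatment group will be utilized"; the denominator is the summed exposure of the group, "where subjects experiencing the respective AE will be censored at the time of occurrence of the AE". The groups listed are "either placebo or CZP 200mg Q2W for the double-blind period or OL-CZP". The exact Poisson interval that follows takes the number of patients with events, and a time t censored at the event. Section 3.6 makes both Total CZP columns AE summary groups.

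**The concern.** Because method-4 exposure is used only for exposure-adjusted incidence, a summed method-4 total has one purpose: to be the denominator of the EAIR in a Total CZP column. If method 4 is run within each period and the results are added, a subject with a first event in the double-blind period is censored there, then adds OL-CZP or SFE time up to a new event or the end of that period. That person is no longer at risk of a first event, so the added time does not belong in a first-event rate. Nothing in Section 11.1 sets the later time to zero.

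The Total CZP columns carry the long-term safety description. If later time is added while each subject is counted once, the pooled rate and both interval bounds fall because of how the denominator is built, and the pooled column can look more favourable than double-blind CZP with no change in risk. This is separate from any question about the length of exposure windows: it remains if every window is aligned.

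**Working it through.** The SAP states no pooled exposure or EAIR value, so there is no figure to reproduce. The check compares the two ways of building the denominator.

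**Inputs from the SAP.** The double-blind period is 52 weeks and the SFE up to 104 weeks (Section 2.3.2), taken as 1 and 2 years. The numerator counts each subject once (Section 11.2).

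**Assumptions, not in the SAP.** Constant hazard L per year; fraction f of double-blind CZP subjects entering the SFE, 0.6 to 0.8, and staying two years; events able to recur; no intervening OL-CZP period.

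**Formulas.** Let q(T) = 1 − exp(−L·T). Per subject:

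- censored once: D1 = [(1 − f)·q(1) + f·q(3)] / L
- summed by period: D2 = [q(1) + f·q(2)] / L

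With the same once-per-subject numerator, the reported rate is the true rate multiplied by D1/D2.

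**Example, L = 0.2.** q(1) = 0.1813, q(2) = 0.3297, q(3) = 0.4512.

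- f = 0.6: (0.4 × 0.1813 + 0.6 × 0.4512) / (0.1813 + 0.6 × 0.3297) = 0.3432 / 0.3791 = 0.905
- f = 0.8: 0.3972 / 0.4450 = 0.893

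| True rate per 100 subject-years | D1/D2, f = 0.6 | D1/D2, f = 0.8 | Understatement |
|---|---|---|---|
| 1 | 0.995 | 0.994 | under 1% |
| 5 | 0.974 | 0.970 | about 3% |
| 20 | 0.905 | 0.893 | 9-11% |
| 50 | 0.807 | 0.779 | 19-22% |

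**The same mechanism in a count.** Take 100 CZP subjects, each with 364 double-blind days (350 + 14) and 728 SFE days, 1,092 in all. Let 20 have a first event on day 182 and no later one.

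- Censored once: 20 × 182 + 80 × 1,092 = 91,000 days = 249.1 subject-years; EAIR = 8.03 per 100.
- Summed by period: 20 × (182 + 728) + 80 × 1,092 = 105,560 days = 289.0 subject-years; EAIR = 6.92 per 100, 14% lower.

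With 5 such subjects instead of 20, the rates are 1.75 and 1.69, 3% lower.

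**If the numerator is summed too.** Adding first events per period gives an expected count of q(1) + f·q(2). Divided by D2 this returns L, so under a constant hazard there is no understatement. But one person can then count more than once, so the count is not the number of patients with events that the Section 11.2 interval requires.

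**The case against.** The strongest reply is that one sentence in Section 11.2 gives both halves of the EAIR. If it governs the Total columns, its censoring clause applies as well as its first-occurrence clause, and no one re-enters. If it does not govern them, the once-only numerator has no source there either. Other text favours single censoring: Section 3.6 makes the Total columns AE summary groups, Section 11.1 censors at the first occurrence without saying within a period, and the interval formula uses censored time. A programmer could add up CZP time and apply the censoring once.

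Much of this stands. A reader might infer that the SAP definitely prescribes a biased pooled rate. It does not: the understatement needs the literal sum combined with a once-per-subject count, and the SAP never states that combination in one place. A reader might also infer that the overall TEAE rate would be badly distorted. The SAP gives no event rate from which to size that row, so the documents cannot support a figure for it.

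The reply does not remove the conflict. The only instruction specific to the Total columns is the sum; it names method 4, and method 4 has no use outside the EAIR. Extending the Section 11.2 principle to those columns makes the two sections disagree, and the list of groups in Section 11.2 does not settle which prevails.

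**Conclusion.** The point holds as an internal conflict. Sections 11.1 and 11.2 give different denominators for the EAIR in the two Total CZP columns, and the literal pooled rule lets censored subjects contribute time again. Whether the reported rates would be too low depends on how the conflict is resolved in programming. On the reading that is too low, the shortfall is about 3%, 9-11% and 19-22% at true rates of 5, 20 and 50 per 100 subject-years, and larger for more frequent events. It is negligible for rare events, which is likely to include most AEs of special interest. The sizes rest on the assumed hazard, recurrence and continuation share.

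The reach is narrow: only EAIRs and their intervals in the two Total CZP columns. The randomized double-blind safety comparison, crude incidences, EAERs and all efficacy results are untouched. It should be corrected, because the text as it stands allows two different answers in the long-term safety tables.

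**What to change.** - **Section 11.1:** limit summation across periods to methods 1 to 3 (2 and 3 for the column that includes the SFE) and to exposure used for the EAER.
- **Section 11.1, method 4 for each Total CZP column:** accumulate the subject's CZP time across the pooled periods up to the first occurrence of the term in any of them, add nothing afterwards, and count the subject once. State the same rule for SOC, HLT and overall TEAE rows, stopping at the first event in that row; the present text asks only for a calculation per preferred term.
- **Section 11.2:** add the SFE and both Total CZP columns to the groups named in the EAIR rule.

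The cost is a few sentences and a minor programming change. Pooled rates will be somewhat higher than under the summed version.

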## 11.2 Adverse events

AE start dates will be examined to determine if they are treatment-emergent and attributable to the double-blind period, open-label period, pre-SFE period or SFE period. AEs occurring either before double-blind study drug administration (pre-treatment) or outside of the windows described below will be defined as non-treatment emergent.

**Table 11–1: Assignment of Adverse Events to Study Periods**

Type of Subject	Assignment Rule Based on AE Start Date	Assignment
Subjects who do not enter the open-label period and do not enter SFE period	Start date is on or after first study drug administration during the double-blind period and on or before the last study drug administration in the double-blind period + 70 days.	Double-blind TEAE
Subjects who do not enter the open-label period but do enter SFE period	Start date is on or after first study drug administration during the double-blind period and on or before the last study drug administration in the double-blind period + 70 days and prior to the SFE period start	Double-blind TEAE

**Table 11–1: Assignment of Adverse Events to Study Periods**

Type of Subject	Assignment Rule Based on AE Start Date	Assignment
Subjects who enter the open-label period	
1. Start date is on or after first study drug administration during the double-blind period and on or before the last study drug administration in the double-blind period + 70 days and before the start date and time of OL-CZP or OL-OT.
 
Note: If a subject continues in the study with OL-OT visits but without taking any relevant other medication, there will be no start date of the other treatment period and all AEs with a start date within 70 days after last administration will be assigned to the DB period.
	Double-blind TEAE
	
2. Start date is on or after the start date of OL-CZP and on or before the last study drug administration in the OL-CZP period + 70 days and
 
 
• before the start date of OL-OT (for subjects moving into OL-OT), or
 
• before the SFE period start (for subjects moving into SFE period)
 
	Open-label CZP TEAE
	
3. Start date is on or after the start date of OL-OT.
 
Note: Other treatment adverse events will not be summarized, but only presented in listings
	Open-label other treatment TEAE
Subjects who enter the pre-SFE period	Start date is after the last double-blind or OL-CZP dose + 70 days and is before the SFE period start.	Pre-SFE AE
Subjects who enter the open-label SFE period	Start date is on or after the SFE period start and on or before the SFE period end + 70 days.	SFE TEAE

If AE intensity or relationship is missing, then the given event will be imputed as severe or related, respectively.

The frequency of all AEs including TEAEs will be presented for each treatment group separately by System Organ Class, high level term, and preferred term. The data will be displayed as number of subjects experiencing the AEs, percentage of subjects, and number of AEs. Certain summaries will also include exposure-adjusted incidence rates and event rates. TEAEs will be summarized by treatment and period as described in [Section 3.6](#).

The following AE summaries will be presented:

- Overview of TEAE
- Overview of Pre-SFE AEs

- TEAE
- Serious TEAE
- Non-serious TEAE
- TEAE with fatal outcome
- TEAE leading to permanent withdrawal of study medication
- Severe TEAE (included in TEAE table by intensity)
- Drug-related TEAE (included in TEAE table by relationship)
- Serious TEAE by relationship
- Non-serious TEAE by relationship
- Fatal TEAE by relationship
- TEAE of special interest (see below)
- TEAE sorted by incidence of PTs in the CZP 200mg group (SOC and higher level term [HLT] will not be utilized)
- Non-serious TEAE with an incidence of more than 5% in 1 of the 2 randomized groups (HLT will not be utilized)
- Non-serious TEAE with an incidence of more than 5% in 1 of the 2 randomized groups by relationship (HLT will not be utilized)
- TEAE subject numbers
- TEAEs with a CZP incidence  $\geq 1\%$  and CZP incidence  $>$  PBO incidence

The AEs of interest and the approach for summarizing them is briefly described below. Further information is provided in the guidance document (AEs of Interest – Cimzia Program 2018-01-05).

1. Serious infections, including opportunistic infections. Serious infections will be summarized using the Serious TEAE table. No separate table is planned. In addition, opportunistic infections (including tuberculosis) will be presented in a table using UCB-defined search criteria.
2. Malignancies, including lymphoma. These will be presented in 2 tables using the Standardized MedDRA Query (SMQ) criteria “Malignant or unspecified tumours” and “Malignant tumours” respectively.
3. Serious cardiovascular events (also called major adverse cardiac events or MACE). These will be presented in a table including all serious TEAEs with the SMQs of “Haemorrhagic central nervous system vascular conditions”, “Conditions associated with central nervous system haemorrhages and cerebrovascular accidents”, and “Ischaemic central nervous system vascular conditions” with the exception of events coding to a PT of “Transient ischaemic attack”, including all serious TEAEs with the HLT of “Ischaemic coronary artery disorders” except events coding to PTs of “Chest Pain” or “Chest discomfort” and including all serious

TEAEs with HLTs of “Heart Failures NEC”, “Left Ventricular Failures”, or “Right Ventricular Failures” and which also code to the SOC of “Cardiac Disorders”.

4. Congestive heart failure. These will be manually identified by the study physician from the TEAE table. No separate table is planned.
5. Demyelinating-like disorders will be presented in table which is based on the SMQ = “Demyelination”. The SMQ search should include all TEAEs which code to a PT included in Scope=Narrow group within the SMQ. TEAEs which code to a PT included in the Scope=Broad group within the SMQ should be excluded from the search.
6. Aplastic anemia, pancytopenia, thrombocytopenia, neutropenia, and leucopenia. These will be presented in a table using the criteria SMQ = “Haematopoietic cytopenias” in the subset of Serious TEAEs.
7. Serious bleeding events. These will be presented in a table using the criteria SMQ = “Haemorrhage terms (excl laboratory terms)” in the subset of Serious TEAEs.
8. Lupus and lupus-like illness. These will be manually identified by the study physician from the TEAE table. No separate table is planned.
9. Serious skin reactions (eg, Stevens-Johnson Syndrome, toxic epidermal necrosis, and erythema multiforme). These will be manually identified by the study physician from Serious TEAE table. No separate table is planned.

The tables for 1, 2, 3, 5, and 6 above, will include the exposure-adjusted incidence rate (EAIR) with associated 95% CI, and the exposure-adjusted event rate (EAER) as described below.

Although not officially AEs of interest, the following events will also be summarized as described in the AEs of Interest – Cimzia Program 2018-01-05 guidance document.

1. Hepatic events. These will consist of a subset of all TEAEs, identified using the following 5 SMQs: Cholestasis and jaundice of hepatic origin; Hepatic failure, fibrosis, and cirrhosis and other liver damage-related conditions; Hepatitis, noninfectious; Liver-related investigations, signs and symptoms; and Liver-related coagulation and bleeding disturbances.
2. Hypersensitivity reactions and anaphylactic reactions. Hypersensitivity reactions will be summarized as any TEAEs occurring on the same day or the day after injection was received, which code to the following preferred terms: Administration site hypersensitivity, Documented hypersensitivity to administered product, Drug hypersensitivity, Hypersensitivity, Hypersensitivity vasculitis, Infusion site hypersensitivity, Injection site hypersensitivity, Medical device site, hypersensitivity, Type II hypersensitivity or Type IV hypersensitivity reaction. Anaphylactic reactions will be defined using an algorithmic approach as described in the “AEs of Interest – Cimzia Program 2018-01-05” guidance document.

Because subjects will be able to adjust background medications during the study, some additional AE tables may be prepared in which events occurring while on certain background medications will be summarized. The list of these supportive tables is expected to be as follows but other subsets of TEAEs may be explored:

- TEAEs reported after starting a new biologic, but within 10 weeks of stopping CZP

- TEAEs reported one month after changing NSAID type
- TEAEs reported three months after changing or adding a DMARD
- TEAEs reported within one month of an addition of oral corticosteroids or 50% increase in dose

The purpose of these tables will be to assess whether any observed treatment differences in the AE profile may be due, in part, to these prespecified background medications.

A TEAE table will also be presented for the ‘anti-CZP antibody status’ subgroup defined in [Section 10](#). Only subjects exposed to CZP and only TEAEs occurring after first dose of CZP will be considered. A further column will be presented summarizing TEAEs occurring after the onset of the positive antibody status. The EAIR will be presented in addition to the associated 95% CI, and the EAER.

The TEAE incidence rates will also be adjusted for exposure (as calculated using methods 3 and 4 in [Section 11.1](#)) and reported by 100 subject years of exposure. Two approaches will be applied to adjust for exposure. One will only use the first occurrence of an AE with corresponding exposure (EAIR) and the second approach will use all AEs and the entire exposure (EAER).

For the EAIR, the first occurrence of an TEAEs for a certain treatment group will be utilized (either placebo or CZP 200mg Q2W for the double-blind period or OL-CZP) and divided by the sum of exposure of all subjects in the respective treatment group, where subjects experiencing the respective AE will be censored at the time of occurrence of the AE. The EAIR will be multiplied by a factor of 100 to give a rate per 100 subject-years.

For the EAER, all TEAEs for a certain treatment group will be utilized (either placebo or CZP 200mg Q2W for the double-blind period or OL-CZP) and divided by the sum of exposure of all subjects in the respective treatment group. The EAER will be multiplied by a factor of 100 to give a rate per 100 subject-years.

The summary of TEAEs, serious TEAEs, and TEAEs leading to permanent withdrawal of study medication will include the EAIR (with corresponding 95% exact CI) and EAER. The confidence interval for the EAIR will be based on Poisson rate CIs. The bounds of the exact 95% CIs are estimated by

$$\text{lower bound} = \frac{1}{2 \cdot t} \cdot \chi^2_{2 \cdot (\text{number of patients with events}), 0.025} \quad \text{and} \quad \text{upper bound} = \frac{1}{2 \cdot t} \cdot \chi^2_{2 \cdot (\text{number of patients with events} + 1), 0.975}$$

$\chi^2_{n,\gamma}$  denotes the chi-distribution with n degrees of freedom and quantile  $\gamma$  and t is the exposure censored at the time of occurrence of the AE.

